### 1.9.2 Substance Use Related Secondary Outcomes

- a) Substance use frequency (count and binary)
- b) Substance Use Severity (continuous)
- c) Self-reported treatment engagement (binary)
- d) Self-reported number of drug treatment sessions (Count)

### 1.9.3 Mediators and Moderators of Outcomes

[figure not shown]
- a) Viral Suppression Moderators: psychological distress (BSI), Housing instability, Food Insecurity Health literacy, HIV-related cognitive problems renal function and liver function.
- b) Viral Suppression Mediators: Medication self-efficacy, Physician-Patient relationship social support and substance use.
- c) CD4 Count Moderators: HCV status.
- d) Drug Use Moderators: Readiness for drug treatment.
- e) Drug Use Mediators: Readiness for drug treatment and social support.

### 1.10 Cost and Cost-Effectiveness Secondary Outcomes

Cost effectiveness analysis, which will not be performed by the DSC, is described separately in the protocol.

#### 1.10.1 Tests of the Secondary Outcomes

Each of the stated secondary outcomes listed in Section 1.9 will be tested separately, using the closed testing procedures described for the primary outcome to control family-wide type I error. The statistical methods used will also mirror the methods used for the primary hypothesis. Those secondary outcomes that are binary will be tested as described for the primary hypothesis using a logistic regression; whereas those secondary outcomes that involve either continuous or ordinal variables will utilize the appropriate distribution and link function. Note that the exact method of analysis will depend on the realized distribution of the particular outcome in this trial for example, an expected count data variable may need to be modeled using a zero-inflated Poisson Regression rather than a Poisson regression if there are too many zero observations to fit the standard Poisson. If there is over-dispersion, a negative binomial (or zero-inflated negative binomial) regression may be appropriate. The hypothesized

moderator variables (for viral suppression: psychological distress, housing instability, food insecurity, health literacy, HIV-related cognitive function, renal function and liver function; and CD4 count. Drug Use moderator: readiness for treatment and HCV status) will be addressed in the same way that the covariates for the planned sensitivity analysis of the primary outcomes (site, age at baseline, race and ethnicity, gender, and primary type of drug use [IV vs. non-IV, opiate vs. non-opiate, and stimulant vs. non-stimulant], baseline level of viral load) will be addressed. Models will be estimated with main effects for these variables, a main effect for randomization group and an interaction between the particular variable and randomized group on the primary outcomes. For these analyses, the overall Type I error will not be controlled, rather, the reader of any resulting journal article will be alerted to the fact that these analyses were the result of *post-hoc* exploratory analyses, and that any statistically significant results may have resulted from a Type I error, and require replication.

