### 1.6.1 Covariates including Site

Randomization should ensure that the distributions of characteristics across our 3 groups are similar at baseline. Thus, the analysis is straightforward, and the primary analysis of association of the particular contrasts of group on the particular outcome will not need to control for covariates, with the exception of an indicator of baseline CD4 count (greater than 350 cells/uL), an indicator of detectable viral load at baseline, and site of recruitment. Site will be included as a covariate because there is the possibility that participants within a site will be more alike than will be participants from different sites. If ignored, this would violate an assumption of the simple model that all observed participants are independent of each other. Inclusion of site as a covariate will correct the model for any dependence in observations within a site, and baseline viral load and CD4 count may prove important predictors. As noted, randomization should control for all other participant level covariates. Nevertheless, to assess the effects of and control for any unintended impact of group differentials across the range of covariates, in a second sensitivity analysis, the simple analysis listed above will be extended to additionally control for age at baseline, race and ethnicity, gender, and primary type of drug use (injection drug use vs. non-injection drug use, and opiate vs. non-opiate, stimulant vs. non-stimulant). The significance levels for any of these covariates will be reported, but will not affect the conclusions of the primary analysis. As listed below, the effects of these variables on viral suppression will be explored more fully in the secondary aims. We will also assess the interaction of each of these covariates with treatment group as they affect the primary outcomes. If statistically significant, the results of these analyses will not affect the p-value of the primary analyses, but may affect our interpretation. However, the results will be reported in the secondary analyses sections.

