### 1.6.2 SAS Code for Primary Analysis

SAS code suitable for performing the primary analysis follows. In this code, it is assumed that non-suppression and death from any cause have been lumped together as outcomes. The p-values from the four contrasts will be used in the closed testing.

```
proc genmod data = all;  
  class arm time patid site vloadbase cd4base;  
  model outcome = vloadbase cd4base site arm time time * arm / dist = bin;
```

```
repeated subject = patid / type = exch;  
contrast "TAU NAV" arm 1 -1 0 time * arm 0 1 0 -1 0 0;  
contrast "TAU NAVCM" arm 1 0 -1 time * arm 0 1 0 0 0 -1;  
contrast "NAV NAVCM" arm 0 1 -1 time * arm 0 0 0 1 0 -1;  
contrast "TAU NAV NAVCM" arm 1 -1 0 time * arm 0 1 0 -1 0 0,  
      arm 1 0 -1 time * arm 0 1 0 0 0 -1;  
run;
```

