### **1.11 Factors for Stratification**

Randomization will be stratified only by site. Site, baseline viral load, and baseline CD4 count will be used as covariates in the primary analysis.

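### Read literally, SAP 1.10.1 gives the substance-use secondary models only site, CD4 and viral load as baseline terms; adding each outcome's own baseline value would gain efficiency at almost no cost

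*SAP*

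**What the plan says.** Section 1.9.2 lists four substance-use outcomes: frequency of use (as a count and as a binary), severity (continuous), self-reported treatment engagement (binary) and self-reported number of treatment sessions (count). It lists no covariates for them.

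Section 1.10.1 states how they are analysed: "The statistical methods used will also mirror the methods used for the primary hypothesis". The latitude it then allows concerns the form of the regression: "Note that the exact method of analysis will depend on the realized distribution of the particular outcome". The examples that follow are zero-inflated and negative binomial models. Covariates are not mentioned there.

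The model to be mirrored is fully described. Section 1.6.1 adjusts for "an indicator of baseline CD4 count (greater than 350 cells/uL), an indicator of detectable viral load at baseline, and site of recruitment". The code in 1.6.2 has the same terms: "model outcome = vloadbase cd4base site arm time time * arm / dist = bin". Section 1.11 repeats the set and ties it to the primary endpoint: "Site, baseline viral load, and baseline CD4 count will be used as covariates in the primary analysis".

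Two variables come near a substance-use baseline. Primary type of drug use enters the sensitivity analysis of viral suppression (1.6.1) as yes/no classes. Readiness for drug treatment is a moderator and mediator of drug use (1.9.3). Neither measures how much or how severely a participant was using at baseline.

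**The concern.** The primary model adjusts viral suppression for a baseline indicator of viral load, that is, for an early form of its own outcome, on the ground in 1.6.1 that it may predict the result. Carried over term by term to substance use, the rule keeps the HIV covariates but drops that reason for having them. Baseline substance use is then absent from the model, and it is not balanced by design either, because randomisation is stratified by site alone (1.11).

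At stake is the efficiency of the substance-use comparisons. Variation in follow-up use that a baseline measurement could explain stays in the error term. There is also a smaller pre-specification issue. Section 1.12 applies no significance adjustment to secondary analyses and relies partly on their having been limited and fixed in advance, so the covariate set of each model should be beyond doubt.

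**Working it through.** **No figure to reproduce.** The SAP states no power, standard deviation, effect size or baseline-to-follow-up correlation for any substance-use outcome. The calculations below show what an own-baseline term would be worth under stated assumptions.

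**Inputs from the SAP.** Section 1.7 gives 266 per arm and simulated attrition of up to 14% (scenarios A and C), so 266 × 0.86 ≈ 229 per arm. Alpha is 0.05, two-sided.

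**Assumptions.** Each outcome is also measured at baseline. For severity, r is its baseline-to-12-month correlation after allowing for the terms already in the model.

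**Continuous outcome (severity).** Adding the baseline value multiplies the residual variance by 1 − r² and the standard error by √(1 − r²). A comparison with 80% power unadjusted then has power Φ[(1.960 + 0.842)/√(1 − r²) − 1.960]. The difference detectable with 80% power is 2.802 × √(2/229) × √(1 − r²) SD.

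| r | Residual variance | Standard error | Power (80% unadjusted) | Detectable difference (SD) |
|---|---|---|---|---|
| 0 | × 1.00 | × 1.00 | 80% | 0.262 |
| 0.3 | × 0.91 | × 0.95 | 84% | 0.250 |
| 0.5 | × 0.75 | × 0.87 | 90% | 0.227 |
| 0.7 | × 0.51 | × 0.71 | 97.5% | 0.187 |

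At r = 0.5 the unadjusted analysis needs 1/0.75 = 1.33 times the participants for the same precision. If deaths also leave the outcome unavailable (14% attrition plus 16% deaths in the TAU arm of scenario A, so 266 × 0.70 ≈ 186 per arm), the unadjusted detectable difference is 0.291 SD. The ratios are unchanged.

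**Count outcome, illustration.** Simulated two-arm negative binomial data, 202 per arm (266 × 0.76, a 24% combined loss), true log rate ratio −0.3, baseline covariate standardised. The strength of association is an assumption.

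| Baseline effect (log rate per SD) | SE without / with baseline | Power without / with |
|---|---|---|
| 0 | 0.111 / 0.111 | 75% / 75% |
| 0.3 | 0.119 / 0.111 | 72% / 77% |
| 0.6 | 0.141 / 0.112 | 56% / 75% |

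**Binary outcome, illustration.** Logistic model, 202 per arm, true conditional log odds ratio 0.6, baseline effect 1.0 per SD. Adding the baseline raised the standard error from 0.201 to 0.223, while the mean estimate moved from 0.495 to 0.605. Power rose from 70% to 78%. The gain is therefore in power. The interval on the log odds scale does not narrow, and the adjusted odds ratio is a different (conditional) quantity from the unadjusted one.

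**The case against.** The strongest reply is that the SAP never lists covariates for the substance-use models. Sections 1.6.1 and 1.11 attach the HIV covariates to the primary analysis, and what follows the mirror rule in 1.10.1 concerns distribution and link. To mirror a model that adjusts for a baseline form of its own endpoint could equally mean using each outcome's own baseline. Section 1.9.2 names no instrument or baseline assessment, and the protocol, not at hand, may do so.

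This stands in part. The SAP does not exclude a baseline value, and a reader who inferred a deliberate exclusion would go too far. But the only model written out has site, CD4 and viral load, and the only stated flexibility is distributional. An analyst who follows the text has no instruction to add anything. On the looser reading the covariates are left open, and the same sentence settles that too.

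Four stronger inferences are not supported:

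- **That every substance-use comparison loses precision.** The loss is nil when baseline does not predict follow-up. Nothing in the SAP shows that it does for treatment engagement or number of sessions.
- **That all intervals are wider than they need be.** The 1 − r² factor applies to severity, the one continuous outcome. Logistic intervals do not narrow with adjustment.
- **That baseline explains most of the between-person variation.** Even r = 0.7 explains 49%.
- **That chance imbalance biases the result.** In a randomised comparison it is already reflected in the standard error.

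**Conclusion.** The point holds as a nearly free improvement to secondary analyses, not as an error that threatens a conclusion. As written, 1.10.1 leads to substance-use models without their own baseline value, and no other section supplies it. The primary analysis is untouched and the secondary comparisons remain valid.

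The benefit is most plausible for frequency and severity. For severity it ranges from a 9% to a 49% fall in residual variance over r = 0.3 to 0.7, and it is nil at r = 0. For counts the illustration gives between no gain and a rise in power from 56% to 75%. For binary outcomes there is a gain in power only. All of this rests on two things the SAP does not state: that the outcome is measured at baseline, and how strongly that measurement predicts follow-up.

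**What to change.** Add to section 1.10.1:

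> Substance use frequency and severity (and any other substance-use outcome measured at baseline) will be modelled with the baseline value of the same outcome (log(baseline + 1) for counts) in addition to site and the primary-model covariates; a missing baseline value will be handled by one pre-specified method, such as a missing indicator.

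The baseline term should be added to the existing covariates, not offered as an alternative to them; otherwise the covariate set stays open to choice. The method for missing baselines should likewise be settled before the data are analysed.

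The cost is one sentence in the SAP and one further model term per outcome. If the outcome is already assessed at baseline, no new data are needed; if it is not, the sentence does not apply to it. The primary analysis and the sample size do not change.

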### **1.10.2 Mediation**

Mediation will be tested using structural equation modeling with Mplus 6.1. These models estimate the effect of the intervention on the potential mediator (path a, e.g., the effect of intervention on *information*) and the effect of the mediator on the outcome or next proximal intermediate outcome (path b, e.g., the effect of *information* on *motivation*). Longer mediation pathways can also be tested (e.g.,  $a*b*c$ ). There is significant mediation if the product of these two paths ( $a*b$ ) is greater than zero. Statistical significance will be assessed using bias-corrected bootstrap confidence intervals on the product terms. This test is by far the most powerful test of mediation and can test multiple mediating pathways within a single structural model.

### **1.10.3 Ancillary Analyses**

All intervention sessions will be audio-taped for quality assurance with the permission of the participant. Approximately 10% of the intervention sessions will be randomly selected and rated for fidelity to the three intervention conditions. A smaller subset, about 15% of the 10% will be rated by two raters. The double rated cases will be used to calculate a kappa statistic to assess the inter-rater reliability of the fidelity instrument. On the full sample of rated intervention sessions, a simple ANOVA will be used to compare the 3 conditions on the ratings of various behaviors performed during the intervention. Depending on the realized distribution of the ratings, a non-parametric test, the Kruskal-Wallis test, may be substituted for the ANOVA procedure. These means and the associated test-statistics will be reported in the primary outcome manuscript and the final report to describe intervention fidelity.

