### **1.3 Treatment Exposure**

Treatment exposure will be summarized by arm and site, comparing the expected with observed number of Patient Navigator sessions attended (only among the two arms where participants randomized to Patient Navigator sessions).

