## 1.7 Rationale for Sample Size and Statistical Power

Power calculations were based on a simulation of several scenarios, with 5000 iterations per scenario. In each iteration, 266 virally unsuppressed participants were recruited to each of three treatment groups, after which death and dropout rates, and rates of suppression before and after 6 months, were imposed so as to result in proportions of simulated participants dead, lost, suppressed, and unsuppressed at both 6 and 12 months as indicated below. These rates characterized the scenario. (Note that the rates dictate the probabilities of joint occurrences of outcomes at 6 and 12 months, but it is possible for more than one set of rates to produce the same set of 6-month and 12-month margins.)

Once these data were simulated, they were subjected to a Generalized Estimating Equation (GEE) analysis in which dropouts were ignored and dead participants were combined with unsuppressed participants. More specifically, the GEE regressed state (suppressed versus unsuppressed or dead) on time (6 months, 12 months), treatment group (Patient Navigator = PN, Contingency Management + Patient Navigator = CM, Treatment as usual = TAU) site (1-10) and the time by treatment group interaction using a binomial link. The outcome of interest was the proportion suppressed (versus unsuppressed or dead) in each arm at 12 months, but the analysis incorporated 6-month data so that the 6-month/12-month correlation could in part offset loss to follow-up between 6 and 12 months. Contrasts were used to obtain p-values for the hypotheses CM=PN=TAU, CM=PN, CM=TAU, and PN=TAU with respect to the outcome of interest.

These p-values were combined together using the closed-testing methodology explained in Section 1.6. Note was taken of which of the pairwise hypotheses were rejected ( $\alpha = 0.05$ , two-tailed), and which accepted according to the Closed testing algorithm in each iteration. Finally, the power for the tests of the various hypotheses was estimated as the proportion of the 5000 iterations in which each hypothesis was rejected.

The scenarios were defined by the following parametric values, which varied from treatment group to treatment group:

- M6 = target suppressed proportion at 6 months (assuming no death or dropout)
- M12 = target suppressed proportion at 12 months (assuming no death or dropout)
- S = Probability that a participant will be suppressed at 12 months, given he was suppressed at 6 months

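### The fidelity test in SAP 1.10.3 treats rated sessions as independent, though they repeat within participants and probably within deliverers (minor; size depends on unstated staffing)

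*SAP*

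**What the plan says.** Section 1.10.3 (Ancillary Analyses) samples sessions, not participants or staff: "Approximately 10% of the intervention sessions will be randomly selected and rated for fidelity to the three intervention conditions". It then fixes the test: "On the full sample of rated intervention sessions, a simple ANOVA will be used to compare the 3 conditions on the ratings of various behaviors". Depending on how the ratings are distributed, "a non-parametric test, the Kruskal-Wallis test, may be substituted for the ANOVA procedure". It names no participant, deliverer or site term, no averaging within clusters and no robust variance. The output is meant for publication: "These means and the associated test-statistics will be reported in the primary outcome manuscript and the final report to describe intervention fidelity".

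Section 1.3 shows that navigator-arm participants are expected to have more than one session, since exposure is summarised by "comparing the expected with observed number of Patient Navigator sessions attended".

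Elsewhere the plan deals with dependence. Section 1.6.1 says of within-site likeness in the primary model: "If ignored, this would violate an assumption of the simple model that all observed participants are independent of each other". The code in section 1.6.2 clusters the primary GEE on the participant. Section 1.10.1 carries the primary methods over to secondary outcomes, but only those listed in section 1.9. Fidelity is not among them, so nothing else in the SAP repairs the test.

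**The concern.** A one-way ANOVA judges the difference between condition means against the spread of single sessions. If sessions from one participant resemble each other, or sessions from one deliverer do, the condition means vary more by chance than that spread implies. The p-value is then too small. Deliverer clustering is the more plausible strong source, because the ratings describe behaviours performed during the session. The rank-based fallback makes the same independence assumption.

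At stake is a published test statistic on fidelity. If deliverers work in one arm only, a difference between a few individuals could be printed as a difference in delivery between conditions.

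**Working it through.** The SAP states no sample size, power or error rate for this comparison, so there is no figure of its own to reproduce. The question is how far the error of the planned test moves from 5% when there is no true difference. The 5% level is borrowed from the primary analysis, because section 1.10.3 sets none.

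**Inputs from the SAP**
- 266 participants per arm and 10 sites (1.7).
- Three conditions and about 10% of sessions rated (1.10.3).
- Randomization stratified by site, so arms are crossed with site (1.11).

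**Assumed, because the SAP does not give them**
- S = 4 or 11 sessions per participant, the same in each arm.
- Participant ICC 0.1–0.5.
- Deliverer ICC 0.05–0.10, with one deliverer per site per arm in the arm-specific case.

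**Formula.** Clustering nested within arm inflates the variance of a condition mean by about D = 1 + (m − 1) × ICC, where m is the number of rated sessions per cluster. With three groups and many sessions the test statistic is close to chi-square on 2 degrees of freedom, whose upper tail is exp(−x/2). The actual error is then about 0.05^(1/D).

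**Participant clustering.** With 10% of S sessions drawn at random, the size-weighted number rated per participant is m = 1 + 0.1 × (S − 1). This is 1.30 for S = 4 and 2.00 for S = 11.

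**Arm-specific deliverers.** m = 0.10 × S × 266 / 10, which is 10.64 for S = 4 and 29.26 for S = 11.

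| Source | S | ICC | D | 0.05^(1/D) | Simulated ANOVA |
|---|---|---|---|---|---|
| Participant | 4 | 0.1 | 1.03 | 5.5% | 4.9% |
| Participant | 4 | 0.5 | 1.15 | 7.4% | 7.0% |
| Participant | 11 | 0.1 | 1.10 | 6.6% | 6.5% |
| Participant | 11 | 0.5 | 1.50 | 13.6% | 12.9% |
| Deliverer, one arm only | 4 | 0.05 | 1.48 | 13.2% | 13.9% |
| Deliverer, one arm only | 4 | 0.10 | 1.96 | 21.8% | 24.2% |
| Deliverer, one arm only | 11 | 0.05 | 2.41 | 28.9% | 29.9% |
| Deliverer, one arm only | 11 | 0.10 | 3.83 | 45.7% | 46.4% |

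The simulations used 3,000 runs per scenario with three conditions. With fully independent sessions they gave 4.7% for ANOVA and 5.1% for Kruskal-Wallis, so they are calibrated. Kruskal-Wallis stayed within about 2 points of ANOVA throughout.

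If only the two navigator arms supply sessions, the lowest deliverer case becomes 2 × [1 − Φ(1.96 / √1.48)], about 10.7%. This is the lower end of the 10–46% range.

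**Cases without large inflation (simulated, S = 11)**
- Deliverers shared across arms: 4.3–5.2%.
- Shared deliverers (ICC 0.1) with participant ICC 0.2 and site ICC 0.1: about 8%.
- Site clustering alone, ICC 0.05–0.2: 4.0–5.7%. A site effect common to all arms cancels from the differences between arms.

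**Check of the remedy.** Site-by-arm mean ratings were analysed with site as a block, under one deliverer per site per arm or one per site shared across arms. The error was 4.3–5.7% in every scenario run. In the same scenarios the planned test gave 5.7–48.5%.

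**The case against.** The strongest reply is that the only repetition readable from the SAP is sessions within participants, and sampling 10% of sessions dilutes it: with S = 4 the error does not exceed about 7%. The large figures need deliverers confined to one arm. The SAP neither states nor excludes that, and staffing commonly belongs to the protocol. The result is ancillary, has no decision rule and is reported as a description. All of this stands, and it limits the size and weight of the point. It does not make an independence test suitable for repeated sessions.

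A reader might infer more, and the SAP does not support it:
- **That the error rate is grossly wrong in general.** With shared deliverers it is near nominal.
- **That site clustering is a cause.** Arms are crossed with site. The warning in 1.6.1 concerns participants in the primary model; here it shows only that the plan recognises dependence.
- **That double-rated sessions enter twice.** Section 1.10.3 assigns them to the kappa statistic and makes the session the unit of the ANOVA. Stating one rating per session is only a clarification.
- **That the p-value will be used to interpret Patient Navigator versus Patient Navigator plus Contingency Management.** The SAP gives its purpose only as describing fidelity.

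**Conclusion.** The point holds as a minor one. Section 1.10.3 fixes a test that assumes independent sessions, the sessions are not independent, and the test statistic is committed to the primary paper and the final report. Under the assumptions listed, the error at nominal 5% is about 5–14% from participant clustering alone and about 10–46% with arm-specific deliverers. With shared deliverers it is about 5%, or up to about 8% once participant clustering is added. Which case applies cannot be settled from the SAP. The primary GEE, its contrasts and the efficacy conclusions are not affected.

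**What to change.** In section 1.10.3, replace the simple ANOVA and its Kruskal-Wallis fallback with one of the following, using one rating per session:
- a mixed model with condition and site as fixed effects and a random effect for the deliverer, plus one for the participant where it can be estimated (with few rated sessions per participant it may not be);
- a comparison of deliverer-level mean ratings within site;
- the condition means reported without p-values, which is enough if the aim is only description.

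The cost is a wording change and a different procedure. For the first two options, each rated session must carry its deliverer and participant identifiers, and the SAP does not say whether these are recorded. Those options also have less power to declare a fidelity difference, most of all when deliverers work in one arm only.
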